10.6.2 Other Safety

Vital Signs

Summaries of vital sign parameters by treatment group will include:

- Each vital sign parameter and change from baseline
- The number (n) and percentage (%) of patients with grade 2 or greater vital sign AEs
- Listings will be provided with flags indicating the AE grade

Laboratory Tests

Clinical laboratory values will be converted to standard international units. Summaries of laboratory variables by treatment group will include:

- Each laboratory result and change from baseline
- The number (n) and percentage (%) of patients with grade 2 or greater laboratory AEs
- Listings will be provided with flags indicating the out-of-laboratory-range values as well

as the AE grade.

Electrocardiogram

12- Lead ECG analyses

Summaries of 12-lead ECG parameters by treatment group will include:

• ECG status (ie, normal, abnormal, clinically significant)

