3.1 STUDY ENDPOINTS

Primary Endpoint:

• Safety and Tolerability

Secondary Endpoints:

- Change in Eczema Area and Severity Index Score (EASI) from baseline to visit 8 EASI score will assess severity and extent of AD with respect to erythema, excoriation, infiltration and lichenification at 4 anatomic sites of the body: lower and upper extremities, trunk and head. The total EASI score shall be in a range (from 0 to 72 points (from no disease to maximum disease severity, respectively).
- Patients (%) achieving Investigator's Global Assessment (IGA) Response (0 or 1) at Visit
 - 8

IGA assesses disease severity and clinical response using a 5-point scale: 0 = clear; 1 = almost clear; 2 = mild; 3 = moderate; 4 = severe. The score is determined by ranking the extent of erythema and papulation/infiltration. A clinical response to therapy will be an IGA score of 0 (clear) or 1 (almost clear). Patients receiving more than one treatment with additional medication to treat AD exacerbation during the study or missing IGA scores at Visit 8 will be treated as non-responders.

- Patients (%) achieving ≥2 IGA Score Reduction at Visit 8
- Pharmacokinetics (PK) Assessment

An enzyme-linked immunosorbent assay (ELISA) has been developed to specifically measure bermekimab levels in human plasma. Blood will be drawn into a single 6 ml Na-Heparin collection tube at each PK collection time point (sample collection is pre-dose at visit 1, visit 3, visit 5, and visit 8). These samples will be collected per the study lab manual and immediately shipped to the Sponsor for PK analysis. The PK samples will also be used to test for the presence of antibodies against bermekimab.

- Change (%) for peak weekly averaged pruritus numerical rating scores (NRS) from baseline to visit 8
- The NRS rating system captures the intensity of patient's itch and pain over a 24-hour period. The following question will be presented to patients: "how would a participant rate his or her itch at the worst moment and on average during the previous 24 hours (scale 0 10 [0 = no itch; 10 = worst possible itch])?" and "how would you rate your pain on average during the previous 24 hours [0 = no pain; 10 = severe pain])?

```
CONFIDENTIAL
```

- Change in weekly averaged peak NRS from baseline to visit 8
- Change in SCORing Atopic Dermatitis (SCORAD) score from baseline to visit 8
 SCORAD was developed by the European Task Force on Atopic Dermatitis

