5.2 STUDY CALENDAR

Visit	Screen	1	2	3	4	5	6	7	8	9
Study Day		0	7 ±2	14 ± 2	21 ±2	28 ± 2	35 ± 2	42 ± 2	49 ± 2	56 ± 2
Informed Consent	Х									
Demography, Height, Weight ^f	х									
Medical History	х									
Infectious Disease Panel +	Х									
IGRA ^e	х									
Serum Pregnancy	Х									
Physical Examination	Х					Х			Х	Х
Urinalysis ▲		Х			Х				х	
Electrocardiogram (ECG)£		Х							Х	
Visit 1 Questionnaire ◆		Х								
Vital Signs ⁺	Х	Х	Х	Х	Х	Х	Х	Х	Х	Х
Urine Pregnancy		Х	х	Х	Х	х	Х	Х	х	
Blood Draw	x ^{ab}	x ^c		xabc		xabc			xabc	
Bermekimab Injection �		Х	Х	Х	Х	Х	Х	Х	Х	
EASI	Х	Х	х	х	Х	х	х	х	х	х
IGA	Х	Х	Х	Х	Х	Х	Х	Х	Х	Х
SCORAD	Х	Х	х	Х	Х	х	Х	Х	Х	Х
DLQI		Х	х	х	Х	х	х	х	х	х
Pruritus/pain NRS ^d		Х	Х	Х	Х	Х	Х	Х	Х	Х
POEM		Х	х	Х	Х	х	Х	Х	х	х
GISS		Х	Х	Х	Х	Х	Х	Х	Х	Х
HADS		X	х	X	Х	X	X	X	X	X
Adverse Events		Х	х	Х	Х	X	Х	Х	Х	х
Concomitant	X	X	х	х	X	х	X	X	Х	х
Meds/Treatments*										

^a Chemistry Panel including: Albumin, Alkaline Phosphatase, ALT, AST, GGT, Bicarbonate (CO2) Calcium,

Chloride, Creatinine, Glucose, Potassium, Sodium, Total Bilirubin, Total Protein, Urea Nitrogen

^b Hematology Panel including: Complete whole blood (WBC, HgB, Platelet, differential)

^cBlood draw for PK and Biomarker analysis

^d Data from patient diary for the previous 7 days to be recorded at this time.

^e Interferon gamma release assay

^fBMI will be calculated at this visit using height and weight

+HIV antibody, Hepatitis C antibody, Hepatitis B panel (HBsAg, anti-HBc, anti-HBs), and interferon gamma release assay (IGRA)

▲ Urinalysis will assess pH, protein, glucose, and blood cells

 \pounds A standard 12-lead ECG will be performed. The ECG strips and/ or reports will be retained with the source documentation.

✤ Each bermekimab injection will be followed by 1 hour monitoring for injection site reaction and vital signs 1 hour post injection (70+/- 10 minutes)

⁺ Vital signs include blood pressure, pulse, oxygen saturation, respiratory rate and body temperature

✦ Assessment of patients Pruritus, Pain and Erythema will be recorded twice [once pre-injection, once post-injection of bermekimab] during visit 1.

* Concomitant medications within 30 days before screening until 7 days after the last administration of the study drug must be recorded for the purpose of drug-drug and drug-disease interaction evaluation and signal detection.

BMI: Body Mass Index [BMI= weight (kg)/height (m²)]
IGRA: Interferon Gamma Release Assay
DLQI: Dermatology Life Quality Index

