7. ASSESSMENT OF SAFETY

Safety will be assessed by monitoring adverse events, vital signs, physical examinations, ECG and clinical laboratory measurements. All subjects who have received at least one dose of bermekimab will be included in the safety analysis. Adverse events will be monitored from Visit 1 (post-infusion) to Visit 9. Any serious adverse events or grade 2 or greater probably or definitely related events will be followed until resolution.

Study drug will be administered under close observation in a facility equipped to handle anaphylaxis. Subjects must be closely monitored until at least 1 hour following the administration of the antibody or 1 hour after their vital signs have stabilized.

Any AE (with the exception of worsening AD symptoms or injection site reactions) of grade 2 or higher must be reported to the sponsor within 24 hours of learning of the event. Any grade 3 or greater injection site reaction must be reported to the sponsor within 24 hours of learning of the event.

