10.5 STATISTICAL METHODS

All analyses will be summarized using descriptive statistics and data will be presented in tabular format for each treatment group and pooling all bermekimab dose groups together. Continuous data will be summarized for each treatment group using the number of observations available (N), means, standard deviation (SD), minimums, medians, and maximums. Categorical data will be summarized for each treatment group using counts and percentages. Missing data will not be categorized in the summaries.

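### The ECG, a component of the primary safety endpoint, is summarised only as a three-level status with no visit, shift table or change from baseline, so offsetting changes and shifts within a category would not be seen in that summary

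*Combined protocol and SAP*

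**What the plan says.** The sole primary endpoint in Section 3.1 is "Safety and Tolerability". Section 7 sets out how it is assessed: "Safety will be assessed by monitoring adverse events, vital signs, physical examinations, ECG and clinical laboratory measurements".

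Sections 5.1 and 5.2 schedule the ECG twice, before the first injection at visit 1 and again at visit 8 (day 49). Section 8.1 defines baseline as the visit 1 assessment before injection. A footnote to the Study Calendar says: "A standard 12-lead ECG will be performed. The ECG strips and/ or reports will be retained with the source documentation".

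Section 10.6.2 treats the three kinds of safety measurement differently:

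- Vital signs: "Each vital sign parameter and change from baseline", plus counts of patients with adverse events of grade 2 or higher, plus flagged listings.
- Laboratory tests: "Each laboratory result and change from baseline", plus the same kinds of counts and listings.
- ECG: the lead-in reads "Summaries of 12-lead ECG parameters by treatment group will include", and the only item under it is "ECG status (ie, normal, abnormal, clinically significant".

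The general rule in Section 10.5 adds no more for this kind of variable: "Categorical data will be summarized for each treatment group using counts and percentages".

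**The concern.** The trial has no control group. Each patient's own visit 1 ECG is therefore the only reference against which an on-treatment ECG can be judged, and the stated summary does not use it. Two kinds of information are lost.

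First, counts of a status do not say who changed. An abnormality present before treatment counts the same as a new one, and a new abnormality in one patient can be cancelled by a resolved one in another. Second, a change in an interval such as PR, QRS or QT that leaves the judged category unchanged leaves no trace.

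The levels are also not clearly exclusive, because a clinically significant ECG is also abnormal. Two sites could code the same tracing differently.

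At stake is whether the report can say, for one named part of its primary endpoint, how many patients had an ECG that worsened on bermekimab.

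**Working it through.** The plan gives no ECG figure, threshold or test to reproduce. The check compares the sections and then counts which outcomes one table can conceal.

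**1. Who can have a pair of ECGs.** The synopsis gives Group A 9 patients and Group B 20, total 9 + 20 = 29. Section 3 follows Group A for 6 visits (to day 35) and Group B for 9 visits (to day 56). The only ECG after baseline is at visit 8.

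- Group A: one scheduled ECG each and no pairs. That is 9/29 = 31% of the trial.
- Group B: two scheduled ECGs each, up to 20 pairs.
- Scheduled tracings: 9 × 1 + 20 × 2 = 49.

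Sections 5.1 and 5.2 do not separate the groups, and Section 10.6.2 promises an ECG summary by treatment group. On the follow-up in Section 3, the Group A column could hold only pre-treatment ECGs.

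**2. What equal counts can hide.** Take Group B with n = 20 and m patients not normal at both visits. If k patients are newly abnormal, k must have resolved, so k can be any whole number from 0 to min(m, n − m).

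| Abnormal at each visit | New abnormalities that fit |
|---|---|
| 2/20 | 0 to 2 |
| 4/20 | 0 to 4 |
| 6/20 | 0 to 6 |

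With m = 4, 16 patients start normal. The two extremes are 0/16 new abnormalities (exact 95% interval 0% to 20.6%) and 4/16 (7.3% to 52.4%). Visit counts of 4/20 and 4/20 are the same for both.

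**3. How easily offsetting could arise.** The documents give no abnormality rates, so these are assumptions. Let A ~ Binomial(16, p) be new abnormalities and B ~ Binomial(4, r) be resolved ones, independent, with p from 5% to 20% and r from 25% to 50%. Given at least one new abnormality, the chance that the visit 8 count is no higher than the baseline count is

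P(B ≥ A | A ≥ 1) = [Σ P(A = a) · P(B ≥ a), a = 1 to 4] / [1 − (1 − p)^16].

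- p = 0.05, r = 0.50: 0.460 / 0.560 = 82%
- p = 0.10, r = 0.25: 0.304 / 0.815 = 37%
- p = 0.20, r = 0.25: 0.146 / 0.972 = 15%

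For 4/20 abnormal at baseline the range is 15% to 82%. It widens to 5% to 94% if the baseline count runs from 2 to 6. Offsetting is thus quite possible when new abnormalities are few and becomes less likely as they become common.

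**4. What would still show.** A net move between categories, say from 4/20 to 10/20 abnormal, would be visible in plain counts (20% to 50%) if status is tabulated by visit. The plan does not say that it will be.

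**The case against.** The strongest reply is that the plan leaves room for more and already covers part of the ground elsewhere.

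- Section 10 describes itself as the basis for the SAP, and the ECG lead-in says what the summaries will include, not all that they will contain. This stands as far as it goes: the text is silent on pairing and does not rule it out. But the same section spells out change from baseline for the two neighbouring measurements and plans nothing comparable for the ECG.
- A new ECG finding reported as an adverse event is captured under Section 9.1. Section 10.6.1 then counts it as treatment-emergent if it develops or worsens after the first dose. This also stands and limits the harm. It depends on the investigator judging the finding reportable and does not reach changes below that threshold.
- Pulse is a vital sign taken at every visit and summarised with change from baseline, so rate is not lost. This stands.
- No numeric interval is said to be entered as data, and a site may hold strips alone. This stands, and it makes a numeric summary optional.
- The study is descriptive. Sections 10.1 and 10.2 state no test for the primary endpoint and a sample of convenience, and no ECG threshold drives escalation or stopping. This too stands, so lost power is not a useful measure here: it would need assumed interval values and tests that the plan does not contain.

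A reader might infer that any treatment-related ECG change would go unseen. The documents do not support that, because net category moves can show in counts by visit and reported events appear in the adverse event tables.

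**Conclusion.** The point holds in a limited form. The only planned summary of the ECG does not relate a patient's visit 8 status to the same patient's visit 1 status. Within that summary, offsetting changes and numeric shifts inside a category would not be seen. The size is up to 4 concealed new abnormalities in Group B if 4 of 20 are abnormal at both visits. That 4/20 is illustrative, as are the rates behind the 15% to 82% range. The conclusion itself needs no assumed rate, because it follows from what Section 10.6.2 lists.

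A second finding rests only on the schedule. As written, 9 of 29 patients have no ECG after baseline, so no within-patient ECG summary is possible for Group A.

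This is a cheap improvement to the summary of a primary safety component. It affects neither the sample size nor the conduct of the trial.

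**What to change.** Replace the single ECG item in Section 10.6.2 with a shift table of ECG status from visit 1 (pre-injection) to visit 8, in patients with both ECGs. Use three mutually exclusive levels: normal; abnormal, not clinically significant; abnormal, clinically significant. State the number of pairs. The cost is a wording change and one table from ECGs already scheduled. Where the status has been recorded with overlapping levels, the coding needs to be clarified.

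Reconcile Sections 3, 5.1, 5.2 and 10.6.2 on Group A. On the stated follow-up the table covers Group B only, up to 20 pairs, and the text should say so.

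Optionally, where the retained reports give PR, QRS and QT, summarise the value and the change from visit 1, with a 95% interval for the mean change. This would bring the ECG into line with vital signs and laboratory values. The small downside is the data entry (at most 2 × 20 = 40 tracings for the Group B pairs) and the noise of local readings. Sites that keep only strips would need someone to read the intervals. The shift table can stand without this part.

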10.7 PK ANALYSIS

Pharmacokinetic analysis of plasma concentrations of bermekimab will be performed for the PK population using non-compartmental model. Standard PK parameters such as maximum concentration (C_{max}) and its occurrence (Tmax), average concentration at steady state (Cavg), area under concentration version time curve from time 0 to selected time point (AUC0-t), elimination rate constant (Kel) and half-life (T1/2), will be presented. Other non-compartmental PK parameter values, as considered appropriate, will be calculated.

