2.6 METHOD OF ADMINISTRATION

The dose of bermekimab for Group A is 200 mg (2ml of the 100 mg/ml formulation) and for Group B is 400 mg (2ml of the 200 mg/ml formulation) administered weekly by subcutaneous injection.

* 45-60 minutes prior to injection, remove the pre-filled syringe from refrigeration and allow it to naturally warm to room temperature before injection. Do not heat the syringe.

Materials Bermekimab pre-filled syringe for injection, warmed to room temperature* Sterile alcohol wipes Band-aids, along with 2x2 gauze bandages and paper tape Latex-free gloves

Injection Site

Determine Injection site, see illustration below:

Abdomen, at least 2 inches away from the belly button, is the recommended injection site for patients with a body mass index (BMI) below 30. (This measurement is calculated at Screening.)

Front Thigh or **Upper Arm** is the recommended injection site for patients with a BMI of **30** or **more**.

(Note: avoid areas where the skin is burned, scarred, hardened, inflamed, swollen, or damaged).

Injection

- Put on gloves
- Wipe injection site clean with alcohol pads
- Raise a fold of skin between the thumb and forefinger (see illustration below).

- Insert needle as illustrated above
- Inject drug slowly
- Withdraw needle. Place band-aid over injection site if necessary (*Note: If bleeding occurs, hold pressure on the injection site for 90 seconds or until bleeding stops, and then apply gauze bandage secured by tape*).

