3. STUDY DESIGN AND OBJECTIVES

Phase 2, open label, dose escalation study of two dose cohorts of bermekimab in patients with moderate to severe atopic dermatitis. The study is multicenter, and will consist of two dose levels: Bermekimab administered subcutaneously at a dose of 200 mg weekly (4 doses) and bermekimab administered subcutaneously at a dose of 400 mg weekly (8 doses). Patients taking the 200mg dose will be followed for 5 weeks (6 visits, day 35 ± 20 , and patients taking the 400mg dose will be followed for 8 weeks (9 visits, day 56 ± 20) to allow for assessment of safety and preliminary efficacy.

Dose escalation details can be found in Section 5.3.

The protocol of the study will be approved by the Institutional Review Board (IRB) or the Ethics Committee (EC) of the participating study sites. Depending on the participating countries, both local and central IRB/EC approvals will be granted. The study will be registered at www.clinicaltrials.gov before the enrollment of the first patient. The trial will be conducted in compliance with the protocol, GCP, and all applicable regulatory requirements.

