refrigeration and lay flat; allow to warm to room temperature. Do not heat

Pre-injection

- Concomitant medications/treatments
- o DLQI
- Urine pregnancy
- o EASI
- o IGA
- HADS
- Pruritus/Pain NRS: data from patient diary to be recorded at this time if available
- o SCORAD
- o POEM
- o GISS
- Vital signs (blood pressure, pulse, oxygen saturation, respiratory rate and body temperature)

Bermekimab subcutaneous injection in accordance with injection site determined by BMI at Screening

Post bermekimab subcutaneous injection

- 1 hour monitoring post-injection
 - Injection reaction
 - Vital signs (blood pressure, pulse, oxygen saturation, respiratory rate and body temperature) one hour post injection (70 +/- 10 minutes)
- Adverse event monitoring

Visit 8 (day 49 +/- 2)

> *At least 45 minutes before injection*: When using pre-filled syringes, remove syringe from

refrigeration and lay flat; allow to warm to room temperature. Do not heat

Pre-injection

- Concomitant medications/treatments
- Urinalysis
- Electrocardiogram (ECG) (patient should be supine for at least 5 minutes prior to performating ECG)
- Physical Examination
- o DLQI
- Urine pregnancy
- o EASI
- o IGA
- o HADS
- Pruritus/Pain NRS: data from patient diary to be recorded at this time if available
- o SCORAD
- o POEM
- o GISS
- Blood draw:
 - chemistry and hematology, 12.5mL
 - PK and Biomarker Analysis, 6mL
- Vital signs (blood pressure, pulse, oxygen saturation, respiratory rate and body temperature)

Bermekimab subcutaneous injection in accordance with injection site determined by BMI at Screening

Post bermekimab subcutaneous injection

- ➤ 1 hour monitoring post-injection
 - Injection reaction
 - Vital signs (blood pressure, pulse, oxygen saturation, respiratory rate and body temperature) one hour post injection (70 +/- 10 minutes)
- Adverse event monitoring

Visit 9 (56 +/- 2)

- Concomitant medications/treatments
- > DLQI
- Physical Examination
- ► EASI
- ► IGA
- > HADS
- > Pruritus/Pain NRS: patient diary to be retained and data to be recorded
- > SCORAD
- > POEM
- ➢ GISS
- Vital signs (blood pressure, pulse, oxygen saturation, respiratory rate and body temperature)
- Adverse Event Monitoring

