6. CORRELATIVE STUDIES

6.1 PHARMACOKINETICS (PK) SAMPLE COLLECTION

An enzyme-linked immunosorbent assay (ELISA) has been developed to specifically measure bermekimab levels in human plasma. Blood will be drawn into a single 6 ml collection tube at each PK collection time point (pre-dose sample collection at visit 1, visit 3, visit 5, and visit 8). These samples will be collected per the study lab manual and immediately shipped to the Sponsor for PK analysis. The PK samples will also be used to test for the presence of antibodies against bermekimab and biomarker analysis.

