10.5.4 Efficacy Analysis

All primary and secondary efficacy analyses will be performed for SAF and PP populations. Summary statistics will be provided to evaluate the overall treatment effect and effect within the treatment group. No statistical comparison of differences will be performed across bermekimab dose groups.

Change from baseline to visit 8 will be summarized using descriptive statistics. Corresponding 95% confidence interval of the point estimate of mean change will be provided by treatment group and for overall pooled population. The number and percent of subjects achieving the response (as specified for the secondary endpoints) will be summarized by treatment groups and overall population along with 95% confidence interval for the point estimate. Number and percent of patients achieving response in EASI, and SCORAD core from baseline at visit 8, will be reported separately, along with 95% confidence interval for 50% or greater reduction.

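### Section 10.7 promises non-compartmental Cmax, Tmax, Cavg, AUC0-t, Kel and half-life, but PK is sampled only pre-dose and Group B (20 of 29 patients) has no sample after its last dose

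*Combined protocol and SAP*

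**What the plan says.** PK is a named secondary endpoint (Synopsis; section 3.1). Section 10.7 commits to a non-compartmental analysis giving maximum concentration and its time, "average concentration at steady state (Cavg), area under concentration version time curve from time 0 to selected time point (AUC0-t"), and adds that the "elimination rate constant (Kel) and half-life (T1/2), will be presented".

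The sampling times are stated consistently. Section 6.1 has "pre-dose sample collection at visit 1, visit 3, visit 5, and visit 8", section 3.1 has "sample collection is pre-dose at visit 1, visit 3, visit 5, and visit 8", and section 8.2 repeats this. The visit lists in section 5.1 place every PK draw among the pre-injection procedures. The calendar in section 5.2 marks PK draws at visits 1, 3, 5 and 8 only and shows no blood draw at visit 9.

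By the Synopsis, Group A (n=9) receives four weekly 200 mg doses at visits 1 to 4, and Group B (n=20) eight weekly 400 mg doses at visits 1 to 8. Visit 8 is scheduled as "Visit 8 (day 49 +/- 2").

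The documents disagree on how long Group A is followed. Section 3 says "Patients taking the 200mg dose will be followed for 5 weeks (6 visits, day 35"), which is before visit 8. The calendar exempts neither group from visits 7 to 9. Section 10.5.4 summarizes change from baseline to visit 8 and then says: "Corresponding 95% confidence interval of the point estimate of mean change will be provided by treatment group and for overall pooled population".

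**The concern.** A non-compartmental half-life needs a declining stretch of concentrations with no dose in between. A non-compartmental Cmax and Tmax need samples near the peak. Cavg and AUC need enough points to follow the curve within dosing intervals. The schedule appears to provide none of these in Group B, and at most a two-point decline in Group A.

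Followed as written, the plan leaves Kel and half-life empty for most patients. It would also publish pre-dose values under the names of peak, time of peak and exposure. Section 1.2 says the study is meant to lay the basis for later randomized trials, so a reader could carry those figures forward as real exposure parameters. No escalation rule (section 5.3) or stopping rule (section 5.6) uses PK, so what is at stake is the PK results and not the conduct of the trial.

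**Working it through.** The plan gives no PK figure to reproduce. The check has two parts: a count that uses only the schedule, and an illustration that needs assumed kinetics.

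**1. Count from the schedule (nominal days)**

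Dose days: Group A 0, 7, 14, 21; Group B 0, 7, 14, 21, 28, 35, 42, 49. PK days: 0, 14, 28, 49, each before any injection that day.

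| | Group A, follow-up to day 35 | Group A, visit 8 attended | Group B |
|---|---|---|---|
| Day 0 | drug-free baseline | drug-free baseline | drug-free baseline |
| Day 14 | 7 days after dose 2 | 7 days after dose 2 | 7 days after dose 2 |
| Day 28 | 7 days after last dose | 7 days after last dose | 7 days after dose 4 |
| Day 49 | none | 28 days after last dose | 7 days after dose 7, before dose 8 |
| Samples after last dose | 1 | 2 | 0 |

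- A log-linear slope needs at least two dose-free points. Group B has none and Group A has one or two. Two points give a slope but no check of linearity.
- The ±2-day visit windows change nothing, because the visit 8 draw still precedes the injection.
- Sample gaps are 14, 14 and 21 days, which is 2, 2 and 3 dosing intervals of 7 days. No dosing interval is sampled at both ends. Tmax can only take the value of a scheduled visit day.
- Group B's share is 20/29 = 69%.

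**2. Illustration (assumed kinetics)**

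The documents give neither a half-life nor an absorption rate. Assume a one-compartment subcutaneous model with half-life 7, 10, 14 or 21 days and ka 0.2, 0.3 or 0.5 per day (12 cases). In units of bioavailable dose over volume, summing over doses given at times x < t:

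C(t) = Σ ka/(ka − ke) · [exp(−ke(t − x)) − exp(−ka(t − x))], with ke = ln 2 / half-life.

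The ratios below do not depend on dose, volume or bioavailability.

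*One case worked through: half-life 14 days, ka 0.3.*

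- Group B concentrations at days 14, 28 and 49 are 1.281, 2.001 and 2.469.
- Trapezoid AUC to day 49 = 14(0 + 1.281)/2 + 14(1.281 + 2.001)/2 + 21(2.001 + 2.469)/2 = 8.967 + 22.974 + 46.935 = 78.88. The model's true AUC is 88.70, so the ratio is 0.889.
- Highest sample over true peak = 2.469/2.750 = 0.898.
- Group A concentrations at days 28 and 49 are 2.0015 and 0.7664. The two-point half-life is 21·ln 2 / ln(2.0015/0.7664) = 14.556/0.960 = 15.2 days, against a true 14.

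*Range over the 12 cases:*

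| Quantity | Group A | Group B |
|---|---|---|
| Trapezoid AUC / true AUC | 0.714–0.910 (to day 28); 0.870–0.949 (to day 49) | 0.771–0.932 (to day 49) |
| Highest sample / true peak | 0.776–0.997 | 0.763–0.924 |
| Reported Tmax against true | day 28 against about 24–27 | day 49 against about 51–53 |
| Mean concentration / steady-state mean | 0.525–0.922 (days 21–28) | 0.762–0.990 (days 42–49) |

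In Group B the day 49 concentration is 1.06 to 1.38 times the day 28 value. Concentrations are still rising, so there is no decline to fit and steady state is not assured. In Group A, if day 49 is sampled, the two-point half-life is 7.1–8.6, 10.2–12.1, 14.2–17.1 and 21.4–26.7 days for true values of 7, 10, 14 and 21, which is 2 to 27% too long.

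A wider assumed range (half-life 5 to 25 days, absorption half-life 1 to 3 days) extends the low end. Highest sample over peak is then 0.62–1.00 in A and 0.62–0.92 in B; the AUC ratio is 0.60–0.91 in A (to day 28) and 0.66–0.93 in B.

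**The case against.** Several points can be made for the plan.

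- *The list is soft.* Section 10.7 introduces the parameters as examples, and section 10 describes itself as the basis for a SAP that may be revised. But the sentence still says the named parameters will be presented, and no analysis wording can create samples that were not drawn.
- *The parameters are not equally affected.* This stands. Kel and half-life in Group B fail on the schedule alone. AUC0-t can be computed, and some assumed cases put it at 95% of true and Group A's Cmax at 99.7% of the peak. At the same parameter values the two groups' ratios differ by only 2 to 6 percentage points for AUC (A to day 28) and 1 to 7 for Cmax. That would support relabelling AUC0-t instead of deleting it. However, with day 0 taken as zero, Group B's trapezoid is just 14·C14 + 17.5·C28 + 10.5·C49, so it adds nothing to reporting the three concentrations themselves.
- *Some Group B patients may stop early* (sections 5.4 and 5.5) and, if they keep attending, give dose-free samples. True, but this would be accidental and selective. The count of 20 applies to patients dosed as planned.
- *Not every sample is a trough.* Correct: visit 1 is a drug-free baseline, and Group A's day 28 draw has no dose after it. This leaves fewer informative on-treatment samples, not more.
- *The stakes are modest.* Also fair. This is a 29-patient convenience sample, and PK is one of many secondary endpoints.

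**Conclusion.** The concern holds. From the schedule alone, Kel and half-life cannot be estimated non-compartmentally in Group B (20 of 29 patients, dosed as planned), nor in Group A if its follow-up ends at day 35. If Group A attends visit 8, at most 9 patients yield a two-point half-life that cannot be checked for linearity. In both groups the reported Cmax would be the highest scheduled sample, Tmax a visit day, and Cavg and AUC0-t summaries of pre-dose values.

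The size of the resulting bias in Cmax, Cavg and AUC0-t cannot be known from the documents. The model ranges depend on the assumed half-life and absorption rate and show only that the bias could be small or substantial. The finding does not rest on them. It should be fixed before PK results are produced; it does not threaten the trial's safety rules or conduct.

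**What to change.** In section 10.7, replace the parameter list with outputs the samples support:

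1. Pre-dose concentration by visit and dose group (geometric mean and CV).
2. The visit 5 to visit 3 concentration ratio within each group.
3. A descriptive 400 mg to 200 mg ratio at visit 5, when each group has had four doses. State that dose is confounded with formulation, since section 2.6 gives Group A "200 mg (2ml of the 100 mg/ml formulation) and for Group B is 400 mg (2ml of the 200 mg/ml formulation").

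Delete Cmax, Tmax, Cavg, AUC0-t, Kel and T1/2 as non-compartmental outputs. Pre-specify any model-based analysis of these sparse data, limit it to what the samples can inform (not Cmax or Tmax), and report its assumptions. Define the PK population that section 10.7 names, because section 10.3 defines only the safety and per-protocol sets.

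Reconcile sections 3, 5.2 and 10.5.4 on whether Group A has a visit 8. Only then state whether a two-point Group A half-life will be reported, labelled exploratory.

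The cost is wording only, with no extra blood draws; the sponsor gives up parameters the schedule cannot deliver. If the sponsor wants to keep Kel and half-life, the alternative is additional PK draws after the last dose, at the cost of extra samples and visits. A draw at the existing visit 9 alone would still leave Group B with a single dose-free point.
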